2.6.3.3 Balance checks

We will perform **randomisation balance checks (descriptive statistics)** on the following covariates:

- Baseline MVPA min per day;
- Baseline daily steps;
- Baseline fruit and vegetables (g/day);
- Baseline fibre (g/day);
- Baseline free sugars (% daily food energy);
- Baseline saturated fat (% daily food energy);
- Age;
- Sex;
- Ethnicity;
- Brand of wearable device.

2.6.3.4 Overall analytical strategy

The entire analysis for this trial is based on an **intention to treat (ITT).** This means that we will assess the impact of being offered any financial incentive (compared to being offered no financial incentives).

In this trial, the unit of analysis is the individual's diet and PA outcomes repeatedly collected over multiple windows of evaluation, and the unit of randomisation is the household. To account for the clustering of observations within individuals and individuals within households, we will use linear mixed-effects models to analyse the impact of being offered any incentive (compared to being offered no incentive) for primary outcomes for both physical activity and diet.

The following table summarises the pre-specified analyses detailed in this evaluation protocol.

Table 11. Pre-specified analyses

Analyses	Research question	Outcome	Analysed	
Primary	Effect of offering financial incentive on PA	MVPA (min/day) Daily steps	Effect at 5m mark; Report	
	Effect of offering financial incentive on dietary behaviour	Fruit and vegetables (g/day) Fibre (g/day) Free sugars (% daily food energy) Saturated fat (% daily food energy)	absolute change	
Secondary	Broader effect of offering financial incentive on holistic constructs	Energy expenditure (kcal/day) Energy intake (kcal/day) Weight (kg) A healthy eating score (1-7)	Effect at 5m mark; Report absolute change	
	Short-term effects on primary outcomes (PA and diet)	MVPA (min/day) Daily steps Fruit and vegetables (g/day) Fibre (g/day) Free sugars (% daily food energy) Saturated Fat (% daily food energy)	Effect at 1m mark; Report absolute change	
	Medium-term effects on primary outcomes (PA and diet)	MVPA (min/day) Daily steps Fruit and vegetables (g/day) Fibre (g/day) Free sugars (% daily food energy) Saturated Fat (% daily food energy)	Effect at 3m mark; Report absolute change	
	Impact of different incentive levels	MVPA (min/day) Daily steps Fruit and vegetables (g/day) Fibre (g/day) Free sugars (% daily food energy) Saturated Fat (% daily food energy)	Effect at 5m mark; Report absolute change	
Expolorator y	Motivation to change behaviours	Motivation to change PA Motivation to change diet	Effect at 5m mark; Report absolute change	
	Subgroup analyses. Analysis by: deprivation level ethnic group	MVPA (min/day) Daily steps Fruit and vegetables (g/day) Fibre (g/day)	Effect at 5m mark; Report absolute	

	 age sex baseline diet baseline PA 	Free sugars (% daily food energy) Saturated Fat (% daily food energy)	change
	Unintended consequences	Self-reported mental well-being measured by WHO-5 Index (0~100, 0 = worst, 100 = best)	Effect at 5m mark;
		Sleep quality (hours/day)	Report absolute change
Sensitivity	Robustness to imputation method (subject to contractual agreement)	MVPA (min/day) Daily steps	Effect at 5m mark; Report absolute change

2.6.3.5 Analytical strategy for the primary analysis

The primary outcomes for physical activity are **MVPA minutes per day and daily** steps at 5 months into the trial (week 21).

We will test for differences between the pooled treatment arms and the control arm five months after randomisation using an intention-to-treat approach and a **linear mixed model (panel regression with random effects)** appropriate for clustered data with repeated measurements, in line with methodology adopted by studies with similar designs^{58,59}. As part of the analytical strategy, we will control for the individual characteristics of age, sex, ethnicity, education, BMI at baseline, the brand of wearable.

The general equation for estimating the model is as follows:

(1)
$$y_{ijd} = \alpha + \beta Treatment_j + \gamma_d + \gamma_W week_{ijd} + \gamma_B baseline_{ijd} + \gamma_M missing. baseline_{ijd} + ... \gamma_X X_{ij} + \delta_{cj} + \delta_{pij} + u_{ijd}$$

 $\delta_{cj} \sim N(0, \sigma_c^2); \ \delta_{pij} \sim N(0, \sigma_p^2) for all i, j; \ u_{ijt} \sim N(0, \sigma_u^2) for all i, j, d$

where:

• y_{iid} is the daily MVPA minutes for participant *i* within household *j* on day *d*;

⁵⁸ Harkins, K. A., Kullgren, J. T., Bellamy, S. L., Karlawish, J., & Glanz, K. (2017). A Trial of Financial and Social Incentives to Increase Older Adults' Walking. *American Journal of Preventive Medicine*, *52*(5), e123–e130. doi: 10.1016/j.amepre.2016.11.011

⁵⁹ Finkelstein, E. A., Haaland, B. A., Bilger, M., Sahasranaman, A., Sloan, R. A., Nang, E. E. K., & Evenson, K. R. (2016). Effectiveness of activity trackers with and without incentives to increase physical activity (TRIPPA): a randomised controlled trial. *The Lancet Diabetes & Endocrinology*, *4*(12), 983–995. doi: 10.1016/S2213-8587(16)30284-4

- *Treatment*_j is a dummy variable taking value 0 for households allocated to the control group, and 1 for households allocated to *any* treatment group;
- γ_d is a fixed effect for the day of the week;
- *week*_{*ijd*} is a categorical variable for the (actual) calendar week that the read is recorded;
- baseline_{ijd} is the value of the outcome on the same day of the last week of the baseline period, approximately five months earlier. Missing values for baseline_{ijd} will be coded as -99 to ensure that we include as many participants as possible;
- *missing. baseline*_{*ijd*} is a dummy variable that equals 1 if *baseline*_{*ijd*} is missing and 0 otherwise and will capture whether MVPA is systematically different for individuals who are missing baseline data for the same day;
- X_{ij} are individual level (including age, sex, ethnicity, education, BMI at baseline, and brand of wearable) and family level covariates we will take missing values for these covariates as separate categories rather than imputing;
- δ_{c_j} are the cluster (i.e. household) level random effects, which have mean zero and follow a normal distribution;
- For each family *j*, $\delta_{p_{ij}}$ are the individual (person) level random effects, which have mean zero within each household and follow a normal distribution;
- u_{ijd} is an idiosyncratic error term. We will use a compound symmetry covariance structure (default for a model with random intercepts).

The primary outcomes for diet are:

- Fruit and vegetables (g/day);
- Fibre (g/day);
- Free sugars (% daily food energy);
- Saturated fat (% daily food energy);

as self-reported in Intake24 recalls at the 5-month follow-up point. We will use a similar model to analyse this outcome, as shown below:

(2)
$$y_{ij} = \alpha + \beta Treatment_{j} + \gamma_{D} weekday_{ij} + \gamma_{W} week_{ij} + \gamma_{N} num. admin_{ij} + \dots \gamma_{B} baseline_{ij} + \gamma_{A} weekday. baseline_{ij} + \gamma_{X} X_{ij} + \delta_{Cj} + u_{ij}$$

$$\delta_{cj} \sim N(0, \sigma_c^2)$$
 for all j; $u_{ij} \sim N(0, \sigma_u^2)$ for all i, j

where:

- y_{ij} is person *i*'s energy intake according to Intake24 surveys at 5 months. If the person took two surveys, we average their reports;
- weekday_{ij} is the proportion of administrations at 5 months that occurred on a weekday (rather than on the weekend). For example, if an individual had one administration on Monday and one on Saturday, weekday. ind_{ij} equals 0.5. This is intended to account for the difference in dietary patterns between

weekdays and the weekend;

- *num. admin*_{ij} is the number of administrations at 5 months (1 or 2);
- baseline_{ij} is calculated in an analogous way to y_{ij}, but for the administration(s) at baseline;
- *weekday.baseline*_{ij} is calculated in an analogous way to *weekday*_{ij}, but for the administration(s) at the baseline;
- All other variables are defined in an analogous way to equation (1). Note that we do not use person-level random effects because there is only one observation per person in the sample.

We are using two primary outcomes, which raises the probability of a false discovery being made on at least one of them. To control for the false discovery rate over primary outcomes, we perform the Benjamini-Hochberg step-up procedure.

2.6.3.6 Analytical strategy for the secondary analysis: Broader effect of offering financial incentive on holistic constructs

The impact of offering incentives (compared to not offering any incentives) on secondary outcomes at the 5 months mark will be assessed using similar methods as the ones for the primary analysis.

2.6.3.7 Analytical strategy for the secondary analysis: Short- and medium-term impacts on primary outcomes

We will estimate the same models as at 5 months (i.e. as in section 2.6.3.5) for the primary outcomes using outcome data from 1 month and 3 months to analyse the average impact of incentives over those shorter time periods. As described above, the three-month outcomes will be the focus for the study should attrition at five months prohibit meaningful analysis at five months.

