2.2.4 Randomisation

Randomisation will be conducted at the household level. This approach has two advantages over individual-level randomisation: (i) avoids the risk of contamination within the same household (but opens up the possibility of additive effects of multiple household members being in treatment together); (ii) reduces the risk that we alienate and / or confuse users in the control group whenever they cohabit with someone assigned to a treatment arm.

Users will enter randomisation only if/when they have completed the baseline phase. This implies that the day of randomisation is different across users even within the same households: it always happens at the end of their baseline phase (if successful), but the exact calendar day depends on when they have downloaded the app, when they have completed the onboarding, and how long it took them to complete the baseline phase (see Figure 1 for an example from a user's perspective).

The randomisation algorithm developed by HUL would then:

1. Check if another user from the same household has already been randomised

¹⁴ We consider the attrition too high if the number of users not providing their data is 10% smaller than expected at the start of the 1 month mark (see Table 6 for the expected attrition at different trial stages).

¹⁵ Results for the 5m mark will still be reported; however, we will rely on results from the 3m mark to provide an assessment of the impact of offering financial incentives.

based on their full addresses (including postcode).

- 2. If YES, the algorithm assigns this user to the same trial arm
- 3. If NO, the algorithm generates a random number from 1-100 (inclusive) for the user.
- 4. Based on the rule described in Figure 2, users are assigned to one of the 4 trial arms. Note that the control arm will be larger than the other arms. This is because at the analysis stage (5m mark), we aim at having 3 users in the control group for each user in the treatment arms. However, we expect attrition to differ across control and treatment groups, as shown in Table 6 in Section 2.4.2.4.. Based on these attrition estimates, at randomisation 12% of users will be assigned to the high incentive arm, 12% to the medium incentive arm, 15% to the low incentive arm, 61% to the control arm.

BIT's in-house IT expert will quality assure the code of the randomisation algorithm developed by HUL before the trial launch.

Figure 1. Onboarding and baseline phase from a user's point of view¹⁶.

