Baseline period	Day 1 of baseline: users are invited to provide their first recall. Users are informed that the first two recalls they will provide (to be provided on two separate days, including information about weight) will be remunerated with a payment of £5 each in points. The second intake24 is optional; users are encouraged to complete the second one within 3 days. The survey will be prominently displayed on the dashboard of the app when users open it for the full duration of the baseline period.	If a user owns a wearable device, they are encouraged to sync their own device with the app and provide their PA data from the first day of the baseline period. If a user orders a wearable device, they are encouraged to sync it with the app and provide their PA data as soon as they receive the device. Users will be nudged for the full duration of their baseline period to wear the device and periodically sync it with the app. In the analysis, we will use all valid daily PA data provided during the baseline period (valid = device worn for at least 6h)
1 month mark (starting the 5th week after randomisation)	 Day 1: users are invited to provide a recall. Users are informed that the first two recalls they provide in the following two weeks will be remunerated with a payment of £5 each in points. Reminders, feedback and survey prominence are repeated as per the baseline phase. In the analysis, we will use all recalls submitted during the 5th and 6th week after randomisation for the 1m mark. 	In the 5th week after randomisation, users will be nudged to wear the device as long as possible for 7 days and sync the device with the app. In the analysis, we will use all valid daily PA data provided during the 5th week after randomisation for the 1m mark. If there are missing values in that week, we will impute them with valid values (if available) on the same day of the week within 2 adjacent weeks (i.e. weeks 3-7).

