2.6.3 Statistical methods

2.6.3.1 Attrition management

Based on the previous literature and on HUL's experience, we expect high levels of attrition (See Section 2.4.2.3).

Attrition (users not providing the wearable device data or not completing Intake24) might happen for multiple reasons (e.g. lack of engagement with data collection, lack of engagement with the app, etc.) at any time. For the purpose of the impact evaluation, our core concern is attrition at the specific measurement points:

- 1 month follow-up;
- 3 month follow-up;
- 5 month follow-up.

We anticipate that differential attrition might occur as participants in the control group might be less incentivised to stay enrolled in the study compared to those in the intervention groups. If the ratio of attrition between the control arm and the pooled intervention arm is greater than or equal to 1.1 (the average relative attrition rate according to a recent meta-analysis on differential attrition of behavioural change interventions⁵³), we propose to adjust for the differential attrition using inverse probability weighting (IPW)⁵⁴, a method proven effective in reducing selection bias for longitudinal studies. The IPW works by modelling the probability of successful retention at 1 month, 3 months and 5 months using baseline observables and then re-weighting those that were retained, so that the reweighted data would be balanced in terms of baseline observables across different arms.

In practice, this means running a logistic regression to calculate the probability of successful retention as a function of baseline variables, getting the fitted probabilities, and then using the inverse of these fitted probabilities as weights in the regression model.

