This imputation process will increase the sample size of person-day observations for the 5-month measurement week, which increases the precision of our estimates. It will also remove (i) reads based on low wear-time which may be underestimating physical activity, as well as (ii) reads that are erroneous due to malfunctioning wearable devices. This imputation process may not fully mitigate the issue that users will be more likely to wear the device when doing more PA (likely to be affected by the treatment assignment). However, we do not think this relationship will be too strong near the 6-hour cut-off point, since historical data on HUL Delta⁵⁷ users suggests that few users (<3%) wear the wearable for less than 6 hours per day on average. Alternative imputation methods that we have considered such as multiple imputation, which takes advantage of the within-subject auto-correlation over time does not fully mitigate against this issue either.

Dietary outcomes

Dietary recalls are provided by users only at key data collection points (baseline, 1 month, 3 months, 5 months). At these data collection points, users are encouraged to provide two recalls in the same week. We do not impute dietary outcomes. If a user provides one dietary recall at a given data collection point, we will not impute the other. If a user provides zero dietary recalls at a given data collection point, we will not impute the not impute either of the recalls since this requires using information that is at least 2 months away.

⁵⁶ The following example provides further clarification. Say that an individual has an invalid read from Monday 16th May, which is at month 5, i.e. 21st week into the trial after randomisation.

[•] If they have a valid read from Monday 9th May or Monday 23rd May, we will take this as the value for Monday 16th May. If they have valid reads for both dates, we will average them.

[•] If they do not have a valid read from Monday 9th May or Monday 23rd May but do have a valid read from Monday 2nd May or Monday 30th May, we will average the available reads from these dates.

[•] If they do not have a valid read from 2nd, 9th, 23rd or 30th May, we will not impute.

⁵⁷ HUL Delta is the name of HUL's own branded wearable device.

For both the primary physical activity and dietary outcomes, we examine the sensitivity of our main findings to different assumptions about missing data (see section 2.6.3.9).

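### The primary dietary model adjusts for the number of 5-month recalls, a post-randomisation behaviour, so its treatment coefficient can depart from the declared intention-to-treat contrast

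*Protocol*

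**What the plan says.** Section 2.6.3.4 declares the whole analysis intention to treat: "This means that we will assess the impact of being offered any financial incentive", compared with no offer.

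Section 2.6.3.5 gives equation (2) for the four dietary primary outcomes. There is one row per person: "If the person took two surveys, we average their reports". The right-hand side has treatment, the weekday share of the 5-month recalls, calendar week, the baseline dietary value and its weekday share, personal covariates, a household random intercept, and num.admin, which "is the number of administrations at 5 months (1 or 2". The weekday term comes with a reason; num.admin does not. All persons share a single residual variance. Sections 2.6.3.7 and 2.6.3.8 carry the model over to 1 and 3 months and to the separate incentive levels.

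The second recall is optional. Section 2.6.3.2 says "users are encouraged to provide two recalls in the same week" and "If a user provides one dietary recall at a given data collection point, we will not impute the other". In Table 9 (section 2.6.1.1) the 1-month row promises that "the first two recalls they provide in the following two weeks will be remunerated with a payment of £5 each in points", and the 5-month row says it works the same way. The payment is described for users in general, not by arm.

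The protocol expects data provision to depend on allocation. Section 2.2.4: "However, we expect attrition to differ across control and treatment groups". Section 2.6.3.1: "We anticipate that differential attrition might occur as participants in the control group might be less incentivised to stay enrolled in the study". The remedy there is inverse probability weighting, with retention modelled from baseline variables.

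**The concern.** Randomisation makes the arms comparable as a whole. It does not make them comparable within groups defined by something participants do afterwards. If the offer brings some less engaged people to a second recall, two-recall users in the incentive arms are a different mix from two-recall users in control, and likewise for one-recall users. If engagement also goes with diet, a coefficient that holds recall count fixed compares unlike people.

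This term sits in the primary model for four of the six primary outcomes. No planned analysis would reveal its influence: the weighting addresses who is retained, not how many recalls a retained person gives, and the sensitivity analyses in section 2.6.3.11 and Appendix D2 vary outlier handling and imputation without ever dropping num.admin.

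A lesser point concerns precision rather than bias. A mean of two recalls is less noisy than a single recall, but equation (2) gives both the same residual variance.

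**Working it through.** **1. The plan's own yardstick.** Inputs: SD 190 g/day (section 2.4.2.1); 2,100 v 2,100, 80% power, Bonferroni division by 4, and 39/41/20% for one, two and three adults (Table 5); household ICC 0.3 and baseline correlation 0.5 (section 2.4.2.2). A two-sided 5% level is assumed, since none is stated, giving 0.05/4 = 0.0125.

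MDES = (2.498 + 0.842) × 190 × √(2/2,100) × √(1 − 0.5²) × √DEFF = 16.96 × √DEFF.

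- DEFF = 1 + (1.81 − 1) × 0.3 = 1.243, with mean size 0.39 + 2 × 0.41 + 3 × 0.20 = 1.81: MDES 18.9 g/day.
- DEFF = 1/(0.39 + 0.41/1.3 + 0.20/1.6) = 1.204: MDES 18.6 g/day.

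The stated 18.7 g/day is reproduced and is not in dispute.

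**2. What the plan says about arm and data provision.** From Table 6, 5-month retention is 2,100/9,400 = 22% in control and 2,100/(1,900 + 1,950 + 2,250) = 2,100/6,100 = 34% with incentives. This is retention in the data at all. The share giving two recalls among those who give at least one is not stated for any arm, nor is any diet difference by recall count.

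**3. Bias formula.** Let γ be the within-arm difference in outcome between two-recall and one-recall users, and P2 the proportion with two recalls. Where the unadjusted contrast is itself unbiased,

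bias from adjusting = −γ × (P2 incentive − P2 control).

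It is zero if either factor is zero. With assumed inputs and SD 190 (0.1 to 0.3 SD = 19 to 57 g/day):

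| Assumed arm difference in P2 | γ = 0.1 SD | γ = 0.2 SD | γ = 0.3 SD |
|---|---|---|---|
| 0 points | 0 | 0 | 0 |
| 2 points | −0.4 | −0.8 | −1.1 |
| 5 points | −1.0 | −1.9 | −2.9 |
| 10 points | −1.9 | −3.8 | −5.7 |
| 20 points | −3.8 | −7.6 | −11.4 |

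Over 5 to 20 points this is 0.95/18.7 = 5% to 11.4/18.7 = 61% of the MDES.

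**4. Simulation check.** 400 runs, 2,100 per arm, true effect 18.7 g/day, one baseline covariate, no household clustering, and a latent engagement score that raises intake. Mean estimates in g/day, Monte Carlo standard error about 0.2:

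| Arm difference in P2 | Engagement–recall link | Without num.admin | With num.admin |
|---|---|---|---|
| 0 | none / weaker / stronger | 18.65 / 18.45 / 18.56 | 18.66 / 18.47 / 18.55 |
| 6 points | none | 18.80 | 18.79 |
| 6 points | weaker | 18.85 | 17.59 |
| 5 points | stronger | 18.75 | 16.69 |
| 11 points | none | 18.66 | 18.63 |
| 11 points | weaker | 18.67 | 16.24 |
| 10 points | stronger | 18.70 | 14.61 |

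The adjusted model drifts only when both links are present. The Monte Carlo standard errors of the two models are almost identical, so dropping the term costs little precision here.

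**5. A case that runs the other way.** If there is no selection but each second recall under-reports by 20 g, with an 11-point arm difference, the model without num.admin gives 17.42 and the model with it 18.50, against a truth of 18.7.

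**The case against.** A reader might infer that the four dietary effects are biased against the intervention, and by a large share of the MDES. The documents do not support that.

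- Table 6 concerns staying in the data. Everyone in equation (2) has already given at least one recall. If only the keenest control users remain, they could complete a second recall as often as incentive users, or more often. A recall payment described alike for all users also gives some reason to expect a smaller gap.
- Large figures need large assumed gaps. Suppose there is no true effect, half of users are engaged and eat 40 to 80 g/day more, and two-recall probabilities for not-engaged/engaged users are 0.3/0.7 in control v 0.5/0.9 with incentives, or 0.4/0.85 v 0.7/0.95. Adjustment then gives −3.5 to −7.4 g/day, 19 to 40% of the MDES. Both settings imply a 20-point arm gap (0.50 v 0.70; 0.625 v 0.825). With 0.4/0.8 in control and a 5-point gap, the same calculation gives −0.9 to −1.7.
- The model without num.admin is unbiased only if the retained arms are comparable. Take assumed retention of 12%/32% (not engaged/engaged) in control and 26%/42% with incentives, which average 22% and 34%, and a 60 g engagement gap. Without weighting, the unadjusted estimate is off by 60 × (0.42/0.68 − 0.32/0.44) = −6.6 g/day. With second-recall probabilities of 0.5/0.8 in both arms, the adjusted one is off by −6.0, slightly nearer the truth.

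All three stand, as does the reporting-artefact case. They limit what can be said about size and direction. They do not supply a reason for the term: the intention-to-treat contrast does not need it, and differential retention already has its own planned remedy.

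**Conclusion.** The point holds in conditional form. The primary dietary model conditions on a voluntary, post-randomisation recall count without giving a reason, and this can shift the treatment coefficient away from the declared estimand. The shift requires both a difference between arms in recall count among responders and a within-arm relation between recall count and diet. The protocol makes the first plausible and quantifies neither.

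The range of about −1 to −11 g/day rests wholly on the assumed 5 to 20 points and 0.1 to 0.3 SD. The negative sign rests on incentives raising second-recall completion and on two-recall users eating more fruit and vegetables. Direction could differ across the four outcomes. No stated sample size or detectable effect changes. This is an avoidable route to bias in the specification, not a demonstration that the dietary results will be wrong.

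**What to change.** Delete the num.admin term from equation (2) for the primary analysis, and therefore from the 1-month, 3-month and incentive-level analyses that reuse it. Keep the person-mean outcome and the baseline dietary mean as covariate. Use household-clustered robust standard errors to allow for the unequal variance of one- and two-recall means. Report the num.admin-adjusted model as a sensitivity analysis, and tabulate the share of responders with two recalls by arm so that readers can judge whether the first link exists.

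A recall-level mixed model with household and person random intercepts and a weekday indicator per recall is a reasonable further sensitivity analysis, but I would not make it primary. It reverses the one-observation-per-person structure in section 2.6.3.5 and still gives two-recall users more weight. In the 20-point illustration above it leaves about −0.1 to −1.8 g/day, assuming 30 to 50% of the variance lies between persons.

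The 5-month weekday share is also post-randomisation, but it has a stated reason and is less clearly a marker of engagement, so I would leave it.

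Cost: one deleted term and a line on standard errors, with no new data, participant contact or change in sample size. The downside is at most a small loss of precision and, if second recalls carry a pure reporting artefact, the loss of an adjustment for it in the primary model. The sensitivity analysis would show that.
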